**Sample size and power analysis:** Given that incidence of overweight/obesity after 2 years (percent of students who were not overweight or obese at baseline but who become overweight or obese) is the primary outcome for the prevention intervention (discussing BMI results/healthful eating/physical activity with students using MI) (**Hypothesis 1a**), calculations are based on the ability to detect a 7.4% incidence difference between the intervention and comparison schools as previously reported from a policy-based school intervention to prevent overweight and obesity. Recruitment of 120 students per school with ~36% who will be overweight or obese and ~64% who will not be overweight or obese (estimated from our previous experience) will give us a total sample of 960 students. Student retention rates in the proposed schools from 9th – 11th grades and from 10th – 12th grades range from 52% to 92% (mean of 72%). In our previous R21, 5% dropped out of the study and 8% left school. Taking into account the schools' retention rates and also our small dropout rate from our previous NIH-funded R21, we are using 35% as the potential attrition rate to calculate a sufficient sample size for testing: 1) BMI result/healthful eating/physical activity discussion with MI component, and also for 2) the weight management component. ~77 students per school are anticipated to be <85th percentile (120 students × 64% who are <85th percentile). If there is 35% attrition, ~50 students per school (400 total) will be available to calculate incidence of overweight/obesity. Based on analysis of our NIH-funded R21 study at two high schools, we used a value of 0.01 for the intraclass correlation (ICC). Therefore, with two-tailed alpha of 0.05 and power level of 0.80, differences of 6% to 10% will be detectable if incidence from the comparison schools range from 7% to 15%, respectively.

Due to higher than anticipated attrition at the high schools from baseline to 1st annual measurements, we will increase our current total sample enrollment (n=960) by 5%, to give a new total sample of 1008 participants.

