For (**Hypothesis 1b**) pre-post measurements of our secondary outcomes (physical activity and dietary intake of sweetened beverages, fat, whole grains, and fruits and vegetables which are continuous variables), we will analyze students with  $\text{BMI} < 85^{\text{th}}$  percentile and students with  $\text{BMI} \geq 85^{\text{th}}$  percentile separately. For students with  $\text{BMI} < 85^{\text{th}}$  percentile, assuming 35% attrition (400 total), ICC of 0.01, two-tailed alpha of 0.05 and power level of 0.80, we will be able to detect an effect size of 0.41, which falls between a small to medium effect size as defined by Cohen. For students with  $\text{BMI} \geq 85^{\text{th}}$  percentile, assuming 35% attrition (224 total), ICC of 0.01, two-tailed alpha of 0.05 and power level of 0.80, we will be able to detect an effect size of 0.51, which is a medium effect size as defined by Cohen.

For (**Hypothesis 2**) the treatment intervention primary outcomes, ~43 students per school are anticipated to be overweight or obese (120 students  $\times$  36% who are  $\geq 85^{\text{th}}$  percentile). If there is 35% attrition, ~28 students will have  $\text{BMI} \geq 85^{\text{th}}$  percentile (overweight or obese) per school (224 total) and be available to calculate difference in BMI z score and insulin resistance (HOMA-IR) after two years. Therefore, we will have 84% power for detecting a difference of 0.16 in two-year BMI z score change between the intervention group and the comparison group. BMI z score change of 0.16 was the change documented in a high intensity ( $>75$  hours of contact) obesity intervention that was cited in the most recent Cochrane review and an evidence report prepared for the US Department of Health and Human Services as one of the best outcomes of intensive lifestyle interventions in children and adolescents. Using data from this study, we will have 80% power to detect a 27% change between the intervention and comparison groups for HOMA-IR.

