- Analysis of intervention effects: Analyses will be conducted in a multilevel framework to account for clustering within schools. Mixed effects linear regression (SAS Proc Mixed) will be utilized for continuous outcomes (e.g., minutes of moderate or vigorous physical activity, BMI z score) and the generalized estimating equation approach (SAS Proc Genmod) will be used for binary dependent variables (e.g., hypertriglyceridemia, prediabetes defined by glucose and hemoglobin A1c) to study intervention impact on physical, behavioral and biochemical outcomes after 2 years. The following main outcomes of interest will be assessed: (**Hypothesis 1a**) Incidence of overweight and obesity after 2 years among students who were not overweight or obese at baseline; (**Hypothesis 1b**) sweetened beverage consumption, fat intake, fruits and vegetable intake, whole grain consumption, and time in moderate and vigorous physical activity after 2 years; (**Hypothesis 2**) BMI z score and HOMA-IR (insulin resistance index score) after 2 years among those students who were overweight or obese at baseline. Additional outcomes that will be assessed in the cohort of students who are overweight or obese at baseline include waist circumference, percent body fat, blood pressure percentiles, and biochemistries (glucose, insulin, hemoglobin A1c, and lipids) after 2 years. Hypotheses will be tested at a 0.05 significance level, two sided. Descriptive statistics (e.g., means  $\pm$  SD, percentages) will be used to evaluate process data. Bivariate relationships of participants' BMI z score change to student attendance will be assessed in the intervention group and a multivariate analysis will be subsequently used to control for other demographic variables. An intention to treat analysis plan will be used. To that end, adolescents who complete a fraction of the sessions will still be accounted for in the analyses. Data imputation methods will be used for missing data. Additionally, we will assess number of sessions completed to determine how attendance is associated with outcomes. The study will assess BMI trends in NM using data from the Youth Risk Resiliency Survey (the NM version of the CDC's Youth Risk Behavior Survey) to evaluate secular trends. The study will use the school's demographic data on race/ethnicity, age, and free/reduced lunch meals to assess the representativeness of the recruited population. If the recruited population does not appear to be representative, we will use weighted data

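### Hypothesis 1a does not have the stated 80% power with 8 schools: a school-level t-test on 6 df has about 56-66%, and the plan names no small-sample method for its GEE test

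*Combined protocol and SAP*

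**What the plan says.** Section V.iii, Sample size and power analysis, says of Hypothesis 1a that "calculations are based on the ability to detect a 7.4% incidence difference between the intervention and comparison schools". It assumes an intraclass correlation of 0.01, 35% attrition and about 50 analysable students per school (400 in total). At two-tailed 0.05 and 80% power it concludes that "differences of 6% to 10% will be detectable if incidence from the comparison schools range from 7% to 15%, respectively". Enrolment was later raised by 5%, "to give a new total sample of 1008 participants", because attrition was higher than expected. Section VI.ii gives 8 schools, with 480 students in each group.

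For Hypothesis 1b, with the same schools, ICC, alpha and power, the same section says "we will be able to detect an effect size of 0.41" for students below the 85th percentile (400 students) and "we will be able to detect an effect size of 0.51" for those at or above it (224 students).

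Under Analysis of intervention effects, "the generalized estimating equation approach (SAS Proc Genmod) will be used for binary dependent variables". The paragraph on baseline covariates that follows assigns the incidence outcome to GEE explicitly. Tests are two-sided at 0.05. No link, test statistic, corrected variance, degrees of freedom or permutation method is named.

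**The concern.** With four schools per arm, the between-school variance is estimated on 6 degrees of freedom. A power calculation that treats this variance as known overstates power. A GEE test that relies on large-sample theory with 8 clusters may not hold its significance level. The Hypothesis 1b effect sizes appear to allow for the few schools, while the Hypothesis 1a differences appear not to.

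Hypothesis 1a is the primary question of the prevention intervention. Depending on the test finally used, the real chance of missing the stated differences is well above 20%, or the real false-positive rate is well above 5%. The plan leaves open which, so neither a null nor a positive result could be read at the stated error rates.

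**Working it through.** **Inputs.** From the plan: two-sided 0.05, power 0.80, ICC 0.01, m = 50 per school, 8 schools. Inferred: 4 schools per arm (480 ÷ 120), hence 8 − 2 = 6 df. Assumed: equal school sizes and no covariate gain.

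**Effective sample size.** Design effect = 1 + (50 − 1) × 0.01 = 1.49. Effective n per arm = 200 / 1.49 = 134.2.

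**Formulas.** Let λ be the expected difference divided by its standard error:
- unpooled: λ = (p1 − p2) / √{[p1(1 − p1) + p2(1 − p2)] / 134.2}
- pooled: λ = (p1 − p2) / √{2p̄(1 − p̄) / 134.2}, where p̄ is the mean of p1 and p2
- arcsine: λ = 2(arcsin√p1 − arcsin√p2) × √(134.2 / 2)

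With normal critical values, power = Φ(λ − 1.96), and 80% needs λ = 2.80. On 6 df, power comes from the noncentral t with critical value 2.447, and 80% needs λ = 3.37.

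**The plan's own figures.** With normal values, the differences detectable with 80% power (arcsine / unpooled / pooled) are 6.07 / 6.43 / 6.50 points at 7% and 9.95 / 10.09 / 10.21 at 15%. These match the stated 6 and 10.

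**The Hypothesis 1b figures.** Detectable effect = λ × √(2 / effective n).
- m = 50: 3.37 × √(2/134.2) = 0.411 on 6 df; 2.80 gives 0.342. The plan states 0.41.
- m = 28 (design effect 1.27, effective n 112/1.27 = 88.2): 0.507 on 6 df; 0.422 with normal values. The plan states 0.51.

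These two figures reproduce only on 6 df.

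**Power at the stated Hypothesis 1a differences** (unpooled / pooled / arcsine):

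| Comparison | λ | Normal values | 6 df |
|---|---|---|---|
| 7% vs 1% | 2.54 / 2.51 / 2.75 | 71.8 / 70.8 / 78.4% | 56.6 / 55.6 / 63.2% |
| 15% vs 5% | 2.77 / 2.73 / 2.82 | 79.1 / 78.0 / 80.5% | 63.9 / 62.7 / 65.5% |

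**Simulation** (beta-binomial, 4 schools per arm, 50 per school, ICC 0.01, 100,000-200,000 runs):

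| Test | Rejects under null | 7% vs 1% | 15% vs 5% |
|---|---|---|---|
| School-level t, 6 df | 5.0-5.1% | about 60% | about 65% |
| GEE logit, uncorrected robust Wald z | about 14% | about 63% | 84% |
| GEE score test, uncorrected | 5.5-5.7% | 62% | 68% |
| GEE logit, bias-corrected (Kauermann-Carroll) variance, t on 6 df | 4.6-4.9% | about 35% | 61% |

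At 7% vs 1%, about 20% of simulated trials gave no finite logit estimate. The last row counts these as non-rejections.

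**Differences with 80% power on 6 df.** At 10% incidence, 8.7-9.3 points. At 15%, 11.4-11.8. At 7%, 6.6 by arcsine and about 6.9 by simulation, both near zero incidence. The pooled and unpooled forms reach only 74-76% even at zero incidence.

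**The 7.4-point target.** The plan gives it no comparison incidence. On 6 df its power is 55-59% if incidence is 10% and 36-37% if it is 15%.

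**1008 enrolled.** 126 × 0.64 × 0.65 = 52.4 per school. Power on 6 df is 57-65% and 64-67%. If attrition is 38%, 126 × 0.64 × 0.62 = 50.0, so the increase only restores the planned number.

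**The case against.** **The basis of the Hypothesis 1a figures is inferred.** This stands. The plan does not say how 6 and 10 were obtained. One-sided testing on 6 df gives 6.1-6.5 and 10.0-10.3 points. Two-sided testing on 6 df with the ICC dropped gives 6.0-6.4 and 9.8-10.1. Each contradicts a stated input, and none of the routes delivers 80% power on all the stated inputs with 6 df.

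**Not all of the shortfall at 7% comes from the few schools.** This also stands. With the pooled or unpooled form, normal values give only 71-72% at exactly 7% vs 1%. So 8-9 of the 23-24 missing points come from rounding 6.4-6.5 down to 6. At 15% rounding explains little.

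**Covariates could recover the power.** The plan puts baseline values in the model. Reaching 80% would require removing 1 − (λ/3.37)² of the variance: 34-44% at 7% vs 1% and 30-34% at 15% vs 5%. Removing all between-school variance would save 1 − 1/1.49 = 33%, which gives 72-80% and 79-82% on 6 df. Recovery is therefore possible in principle, but the plan quantifies no gain and its power figures claim none.

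**Two stronger readings are tempting.** A reader might infer that any test holding 0.05 has 56-66% power. That range belongs to the 6-df formulas and the school-level t-test; the bias-corrected GEE also holds 0.05 and has about 35% at 7% vs 1%. A reader might also infer that the trial will run at a 14% false-positive rate. That holds only for an uncorrected robust Wald z test, and the plan does not say that it will use one.

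**Conclusion.** The 80% power stated for Hypothesis 1a is not supported on the plan's own inputs. A school-level t-test on 6 df has about 56-63% power at 7% vs 1% and 63-66% at 15% vs 5%, so it would miss the stated differences about 34-44% of the time rather than 20%. None of the four tests examined combines 80% power with a 5% error rate, so the conclusion does not depend on guessing which GEE test was meant.

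It rests on 4 schools per arm, about 50 analysable students in each, ICC 0.01 and no credited covariate gain. Unequal school sizes change little: 36, 45, 55 and 64 per arm (an assumption scaled from the plan's 52-92% school retention) give 58% and 64% by simulation. That the plan used normal critical values for Hypothesis 1a and 6 df for Hypothesis 1b is the reading that best fits its figures, not something it states.

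**What to change.** 1. Before analysis, name for Hypothesis 1a a test that is valid with 8 clusters. One example is a t-test on 6 df comparing school incidence proportions, covariate-adjusted if wanted. If GEE is kept, state its link, small-sample method and own power. Make the change both under Analysis of intervention effects and in the baseline-covariate paragraph that assigns incidence to GEE, and reconcile it with the missing-data text there.

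2. Restate the Hypothesis 1a power for the named test. For the school-level t-test at about 50 per school, 80% power needs about 8.7-9.3 points at 10% incidence and 11.4-11.8 at 15%. At 7%, say that 6 points has about 56-63% power and that 80% is reached only near zero incidence or, by the pooled and unpooled forms, not at all. These figures do not carry over to a bias-corrected logit GEE.

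3. Give the power for the 7.4-point target by assumed incidence (for the school-level t-test, about 55-59% at 10% and 36-37% at 15%), and say whether the figures use 960 or 1008 enrolled.

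The cost is less favourable stated power, a stricter test than an uncorrected Wald z, and a change or addition to the named GEE analysis. No students, schools or visits are added. Enrolment and the first annual measurements had already begun, so restating power changes no design feature. Naming the test is the part that protects the inference, and it has to be done before outcomes are seen.

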Analysis Plan: As a preliminary step, we will examine the skewness and kurtosis of all variables to assure no problematic deviations from normality. In the event of such deviations, we will use appropriate transformations or use non-parametric methods. Analyses will be conducted using SAS Version 9.3, STATA Version 12 and Mplus Version 5. All programs include capabilities to test models with categorical outcomes, missing data, and to account for a design that uses a multilevel or clustered framework.

- Pretest equivalence: To explore the possible size and direction of bias that may exist, the pretest equivalence of conditions across demographics, BMI percentile, and other outcome variables of interest will be assessed via t-tests on continuous items and  $\chi^2$  tests of categorical items from the pretest. Wilcoxon rank sum tests or appropriate transformations will be used for non-normal data. We will use the Bonferroni approach to correct for alpha inflation with an experiment-wise alpha of 0.05. For variables where there are significant differences, the baseline values will be included as covariates in the analysis of intervention effects.

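### The pretest equivalence tests ignore school clustering, so their stated experiment-wise 0.05 is not held and any extra covariates they select are chosen by tests of the wrong size

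*Combined protocol and SAP*

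**What the plan says.** The trial randomises schools: eight of them, with 480 students per arm (Section V.i, Research Design; Section VI.ii). Four statements in Section V.iii bear on the point.

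- **Pretest equivalence, method.** Demographics, BMI percentile and "other outcome variables of interest will be assessed via t-tests on continuous items"; categorical items get chi-square tests, and "Wilcoxon rank sum tests or appropriate transformations will be used for non-normal data". A Bonferroni correction is applied "to correct for alpha inflation with an experiment-wise alpha of 0.05". The number of variables is not given.
- **Pretest equivalence, consequence.** "For variables where there are significant differences, the baseline values will be included as covariates in the analysis of intervention effects".
- **Outcome models.** For the effect estimates themselves, the plan does allow for schools: "Analyses will be conducted in a multilevel framework to account for clustering within schools". This sentence sits under the intervention-effects bullet. For the pretest tests, the nearest statement is the opening remark of the Analysis Plan that the software can handle clustered designs.
- **Covariates fixed without a test.** The closing paragraph on the models includes baseline values in both the mixed and the GEE models, and a repeated-grade covariate for students who repeat. Neither depends on a pretest result.

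The Research Design paragraph in Section V.i also relies on the pretests to judge how large any bias may be and in which direction it runs.

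**The concern.** Students in one school tend to resemble each other, so a difference between two groups of four schools varies more by chance than a difference between two groups of 480 independent students. A t-test, chi-square test or rank sum test that ignores this uses too small a standard error. Bonferroni does not repair that: it divides the nominal alpha, but each test still exceeds its share.

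Two things are at stake. First, the bias assessment may present chance differences between schools as evidence that the arms are not equivalent. Second, the same tests decide which covariates enter the effect models beyond those fixed in advance. Significance is a poor criterion for that choice even with correct tests, because it measures how unlikely an imbalance is and not how strongly the variable predicts the outcome.

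**Working it through.** **Inputs from the documents.** ICC 0.01, and "Recruitment of 120 students per school" (Section V.iii, Sample size and power analysis). The same paragraphs anticipate about 77 students per school below the 85th percentile and about 43 at or above it. Enrolment was later raised "to give a new total sample of 1008 participants", which is 1008/8 = 126 per school.

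**Assumptions.** The number of pretest variables k is not stated; 10, 20 and 30 are shown. ICC 0.01 is applied to every baseline variable, with a range below. Schools are of equal size, four per arm. Variables are independent for the experiment-wise rate; correlation would lower that rate but not the inflation of each test.

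**Step 1: the plan's own figure.** Bonferroni gives k × (0.05/k) = 0.05 as an upper bound. With 20 independent variables and ICC 0, the exact value is 1 − (1 − 0.0025)^20 = 4.9%. The stated 0.05 therefore holds if students are independent.

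**Step 2: does the plan count clustering elsewhere?** Detectable effect = (t(0.975) + t(0.80), 6 df) × √(2 × DEFF / n per arm), with DEFF = 1 + (m − 1) × ICC.

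- 400 students, 50 per school: DEFF = 1.49; (2.447 + 0.906) × √(2 × 1.49/200) = 0.41, as stated.
- 224 students, 28 per school: DEFF = 1.27; 3.353 × √(2 × 1.27/112) = 0.505. The noncentral t gives 0.507; the plan states 0.51.
- Without clustering and with normal quantiles the values would be 0.28 and 0.37.

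So the power section allows for clustering and the pretest tests do not.

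**Step 3: true size of one unadjusted test.** Size = 2 × [1 − Φ(z / √DEFF)]. With 120 per school, DEFF = 1 + 119 × 0.01 = 2.19 and √DEFF = 1.480. At nominal 0.05: 1.960/1.480 = 1.324, size 0.185. At 126 per school DEFF is 2.25 and the size is 0.191.

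**Step 4: after Bonferroni, 120 per school.** Experiment-wise rate = 1 − (1 − true size)^k.

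| k | nominal per test | z | true size per test | experiment-wise |
|---|---|---|---|---|
| 10 | 0.005 | 2.807 | 0.058 | 45% |
| 20 | 0.0025 | 3.023 | 0.041 | 57% |
| 30 | 0.0017 | 3.144 | 0.034 | 64% |

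**Step 5: if balance is tested within BMI strata, k = 20.**

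- 77 per school: DEFF 1.76, true size 0.023, experiment-wise 37%.
- 43 per school: DEFF 1.42, true size 0.011, experiment-wise 20%.

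**Step 6: sensitivity to the ICC, k = 20, 120 per school.** ICC 0 gives 4.9%, 0.005 gives 29%, 0.01 gives 57%, 0.02 gives 88%, and 0.05 gives over 99%.

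**Step 7: simulation check.** In 200,000 trials at ICC 0.01 with 120 per school, the unadjusted test rejected 0.184 of the time at nominal 0.05 and 0.040 at nominal 0.0025. A t-test on the eight school means (6 df) gave 0.049 and 0.0024.

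**Step 8: what the rule leaves unadjusted.** With k = 20 and 480 per arm, a continuous variable is flagged only if its observed difference exceeds 3.023 × √(2/480) = 0.195 SD. A smaller observed difference is not flagged, however prognostic the variable.

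**The case against.** The strongest reply is that little in the primary analysis depends on these tests. Three parts of it stand.

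- **Not the whole adjustment set.** A reader might infer that the tests decide all the covariates. The documents do not support that: baseline values and repeated grade enter regardless. Only additional covariates depend on the tests. For Hypothesis 1a the protection is thinner, because every student in that cohort is below the 85th percentile at baseline. Baseline overweight status is then constant, and the plan does not name baseline BMI z score in its place.
- **Not selection on outcomes.** A reader might infer that covariates are picked after results are known. The rule is written in advance and uses baseline data.
- **Not an inflated intervention test.** A reader might carry the 18.5% or 57% over to the treatment comparison. The outcome models are multilevel, and nothing in the documents shows inflation there. In a simulation of the rule under no intervention effect (20 independent covariates, three of them prognostic at 0.3 SD, a school-level 6-df test, 50 or 120 per school, ICC 0.01 or 0.05, all assumed), the intervention test rejected in 4.3% to 4.8% of trials.

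It can also be said that under randomisation every imbalance is chance, that adjusting for a realised one does no evident harm, and that over-flagging partly offsets Bonferroni's strictness. That is fair as to harm. It does not rescue the stated 0.05, nor a bias assessment that reads these tests as evidence of non-equivalence. Two errors that partly cancel are also no basis for choosing covariates.

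**Conclusion.** The point holds for the pretest tests and for the covariates they add. As written, those tests do not hold the experiment-wise 0.05 at the plan's own ICC. One test at nominal 5% has a true size of about 18.5% in the full sample. The experiment-wise rate is roughly 45% to 64% for 10 to 30 variables there, and 37% or 20% within the two BMI strata with 20 variables. The single-test figure rests on ICC 0.01 and equal schools. The experiment-wise figures also need the assumed number of variables and their independence, so their exact level is uncertain; the direction is not, for any positive ICC.

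The consequence is limited: a balance report that may mislead, and additional covariates selected by significance with tests of the wrong size. The plan also makes baseline values conditional in one place and unconditional in another, and these statements need reconciling. It is worth correcting because the rule is wrong as stated and the repair is cheap, not because the intervention result is shown to be at risk.

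**What to change.** - Delete the rule that turns a significant pretest difference into a covariate, and reconcile the Pretest equivalence bullet with the later paragraph that includes baseline values unconditionally.
- Before outcome analysis, fix the covariates on prognostic grounds. Keep the baseline value of the outcome and repeated grade. For Hypothesis 1a, name baseline BMI z score. Add any demographics already collected that the sponsor judges prognostic, and keep the list short given eight schools.
- Describe baseline balance by arm and by school with means, SDs and standardised differences. If tests are kept, use school-level or clustered tests and state how many variables are tested.

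The cost is analysis-plan wording. Demographics, height and weight are already collected at baseline, so no new data and no change to the conduct of the trial are needed.

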
analysis procedures to estimate outcomes for the school population.

Baseline values will be included as covariates in the mixed effects linear regression models for continuous dependent variables and the generalized estimating equation models for binary dependent values including the incidence of overweight or obesity or the presence or absence of specific components of the metabolic syndrome. For students who repeat grades, we will include "repeated grade" as a covariate. Intervention (coded 0=control and 1=intervention) will be entered as a fixed effect into the multilevel models predicting outcomes. One equation will be estimated for each of the outcomes of interest. This approach is conceptually identical to an analysis of variance or covariance (ANOVA or ANCOVA) but has two distinct advantages. First, it allows for the analysis of clustered data, and second, it avoids list-wise deletion of subjects with missing assessments. The model relaxes the restrictive assumption that the data are missing completely at random and provides unbiased estimates under the less restrictive assumption of missing at random. This approach to missing data, i.e., the use of techniques that include full information maximum likelihood estimation of missing values, will be used.

• **Analysis of semi-structured Interviews (Aim 3):** Parent and student interviews conducted following the intervention will be analyzed using standard qualitative assessment methods. [name] will lead this analytic process. The interviews will each be transcribed and distributed to the research team. Each member will review transcripts independently, identifying themes related to the stem questions as well as other emergent areas of interest. The analysis will proceed in an iterative fashion, with the team reviewing sets of 3 to 4 transcripts in each category (parent and student). Following the independent reading, the team will meet to list the full range of themes, identify anomalous or unanticipated findings, and revise the interview guides accordingly. This process will continue until the team has reached consensus. At that stage, the thematic list will be converted into a template for coding purposes. Interviews will be coded in NVivo 9 (Melbourne, Australia), a qualitative data analysis software package, at which point queries to refine analytic and interpretive understandings will be conducted.

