## VI. Human Subjects:

i) Describe characteristics (inclusion criteria) of subject population, including precautions to be taken with vulnerable populations (e.g. children, prisoners, mentally ill/disabled person). Answer for each subject group, if different.

Inclusion criteria are as follows: 1) enrolled in 9th or 10th grade at the participating school, and 2)

informed written assent and informed written parent/guardian consent to participate in the full study for two years.

Research nurses or phlebotomist and clinical providers who are familiar with working with children and adolescents are used to collect data in this study. Data collection will be done in a private setting. Parental consent and adolescent assent is required prior to participation.

ii) Provide approximate number of subjects (both control and intervention groups).

A total of 960 high school students in the 9th and 10th grades (ages 14-17 years) will be recruited from 8 high schools to participate (480 in the intervention group and 480 in the comparison group); students will be followed until they are in the 11th and 12th grades, respectively. Enrollment will end when samples are met.

Due to higher than anticipated attrition at the high schools from baseline to 1st annual measurements, we will increase our current total sample enrollment (n=960) by 5%, to give a new total sample of 1008 participants.

iii) What characteristics (exclusion criteria) would exclude subjects, who are otherwise eligible, from this study? (Answer for each subject group, if different.)

Exclusion criteria are as follows: 1) blood pressure in the range of stage 2 hypertension in which an immediate medical assessment for pharmacotherapy is required, 2) diabetes, 3) use of oral or injectable corticosteroids or antipsychotics, 4) inability to perform moderate to vigorous physical activity, 5) not ambulatory, 6) medications for the control of diabetes, hypertension, and hyperlipidemia (or high cholesterol), 7) a score of 20 or more on the EAT-26 screening measure, and 8) developmental disorders that affect weight or the ability to understand the study procedures or counseling.

Students who meet withdrawal criteria (e.g., pregnancy) will be offered care in the SBHC.

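### With 8 schools, the GEE test of the prevention primary outcome (Hypothesis 1a) has no stated small-cluster method; one reading the wording allows, an uncorrected Wald z-test, has about 14% type I error

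*Combined protocol and SAP*

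**What the plan says.** Section V.iii, Analysis of intervention effects, assigns the method for binary outcomes: "the generalized estimating equation approach (SAS Proc Genmod) will be used for binary dependent variables". The same section later refers to "generalized estimating equation models for binary dependent values including the incidence of overweight or obesity", so Hypothesis 1a is included. The sample size section calls this incidence the primary outcome of the prevention component. The test level is set by "Hypotheses will be tested at a 0.05 significance level, two sided". Clustering within schools is to be accounted for. Further covariates may enter after the pretest comparison: "For variables where there are significant differences, the baseline values will be included as covariates in the analysis of intervention effects".

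Section VI.ii says students "will be recruited from 8 high schools to participate (480 in the intervention group and 480 in the comparison group". At the planned 120 per school, 480 per arm means 4 schools per arm; the split is inferred, not stated.

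No section gives the variance estimator, the choice of Wald or score test, the z or t reference, the degrees of freedom, a small-sample correction, or a school-level analysis.

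For Hypothesis 1a, the sample size section states 80% power at two-tailed 0.05 with ICC 0.01 and about 50 evaluable students per school: "differences of 6% to 10% will be detectable if incidence from the comparison schools range from 7% to 15%, respectively". For Hypothesis 1b in students below the 85th percentile it states "we will be able to detect an effect size of 0.41". For the heavier group it gives 0.51.

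**The concern.** The GEE sandwich variance and its normal reference rely on many clusters. Four per arm is far too few: the variance estimate is biased downward and is itself imprecise. The error rate of the test therefore depends on details that the plan leaves open. Settling them after the data are seen could decide whether the primary prevention result is called significant. Planned power is affected too, because a test with the right error rate on 8 schools detects less than a normal-reference calculation suggests.

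**Working it through.** **Inputs.** From the plan: 8 schools, 50 evaluable students per school (28 in the heavier group), ICC 0.01, two-sided 0.05, 80% power. Inferred: 4 schools per arm, hence 8 - 2 = 6 degrees of freedom. The closed form in step 3 assumes equal school sizes.

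**1. The plan's Hypothesis 1a figures.** Design effect = 1 + 49 × 0.01 = 1.49, so effective n per arm = 200/1.49 = 134.2. With a normal reference, the decrease detectable at 80% power is:

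| Formula | From 7% | From 15% |
|---|---|---|
| Pooled | 6.5 points | 10.2 points |
| Unpooled | 6.4 | 10.1 |
| Arcsine | 6.1 | 9.9 |

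All round to the stated 6 and 10. On 6 df the arcsine formula gives 6.6 and 11.4, and the unpooled formula gives 11.6 from 15%. The unpooled formula is unreliable near zero incidence and is not used on 6 df from 7%.

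**2. The plan's Hypothesis 1b figures.** Detectable effect = (sum of critical values) × sqrt(2 × DE/(4m)).

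- m = 50, DE 1.49: on 6 df, (2.447 + 0.906) × 0.1221 = 0.409; normal reference, 2.802 × 0.1221 = 0.342. Stated: 0.41.
- m = 28, DE 1.27: on 6 df, 3.353 × 0.1506 = 0.505; normal reference, 0.422. Stated: 0.51.

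Of the two references, only 6 df reproduces these values. No formula is named in the plan, so it is an inference that the power section mixes the two.

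**3. Type I error under each reading.** With 4 equal schools per arm, the uncorrected sandwich variance of an arm mean is (sum of squared school deviations)/16. The unbiased form is the same sum divided by 4 × 3 = 12. The ratio is 12/16 = 3/4.

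- Uncorrected variance, z: 2 × P(t6 > 1.96 × sqrt(3/4)) = 2 × P(t6 > 1.697) = 14.05%. Interval coverage is therefore about 86%.
- Uncorrected variance, t6: 2 × P(t6 > 2.447 × sqrt(3/4)) = 7.8%.
- Unbiased variance, z: 2 × P(t6 > 1.96) = 9.8%.
- Unbiased variance, t6: 5.0%.

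**4. Check by simulation.** Null beta-binomial data, 8 schools of 50, incidence 7-15%:

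- The uncorrected Wald z-test rejects in 13.4-14.8% of trials for ICC 0 to 0.03.
- At ICC 0.01, the robust score test runs at 5.5-5.6%, Kauermann-Carroll with t6 at 4.7-4.8%, Mancl-DeRouen with t6 at 2.7-2.8%, and a school-level t-test on 6 df at 5.0%.
- A fitted exchangeable GEE with empirical-SE z gives 13.6% unadjusted and 16.0% with a baseline covariate of assumed strength.
- Assumed unequal school sizes (30-70 or 20-80) give 14.9-16.4%.

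**5. Power at exactly the stated differences.** Normal reference: Φ(δ - 1.96). On 6 df: P(|T| > 2.447), with T noncentral t and noncentrality δ. For 7% v 1%, δ = 2.54 unpooled and 2.75 arcsine. For 15% v 5%, δ = 2.77 and 2.82.

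| Comparison | Normal reference (unpooled / arcsine) | 6 df, formula | 6 df, simulated school-level t-test (raw / arcsine) |
|---|---|---|---|
| 7% v 1% | 72% / 78% | 63% (arcsine) | 60% / 68% |
| 15% v 5% | 79% / 81% | 64% / 66% | 65% / 65% |

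The loss due to 6 df is about 15 points by formula. At 7% v 1% the remaining gap from 80% is rounding of the stated difference: exactly 6 points does not reach 80% even on a normal reference.

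**6. Interval width relative to the uncorrected Wald interval.** Unbiased variance with t6: 2.447/(1.96 × sqrt(3/4)) = 1.44. Mancl-DeRouen with t6: (4/3) × 2.447/1.96 = 1.66.

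**The case against.** The strongest reply is that the 14% belongs to one reading only. The plan does not declare an uncorrected Wald z-test. A robust score test fits the same words and runs at about 5-6%, and the Hypothesis 1b effect sizes suggest that the planners used school-level degrees of freedom at least once. That stands. A reader might infer that the trial will run at 14%, or that clustering is ignored. The documents support neither: the test is left open, and clustering within schools is explicitly modelled. What remains is that nothing in the plan excludes the 14% test, and that a score test would leave a Wald interval with about 86% coverage.

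A second reply is that an ICC of 0.01 is too small to matter. It does not stand. The inflation is much the same at ICC 0, because it comes from the number of schools. A model-based exchangeable SE with a z reference does not help either (13.3% in the fitted GEE).

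A third reply is the larger enrolment: "we will increase our current total sample enrollment (n=960) by 5%, to give a new total sample of 1008 participants". That adds students, not schools, so 6 df remain. The stated reason is attrition above expectation, so a gain in evaluable students or in power cannot be assumed.

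Finally, the mixed models for continuous outcomes also lack stated degrees of freedom, so one could call this a general want of detail. That is fair. Those models were not quantified here, and the point is confined to the binary outcomes.

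**Conclusion.** The concern holds as a missing specification with a measurable consequence. Among the tests that the wording permits, the true level ranges from about 3% (Mancl-DeRouen with t6) to about 14% (uncorrected Wald z). The 14.05% is exact for 4 equal schools per arm under a normal approximation to school means. Unequal school sizes or covariates raised it to about 16% under the assumptions tried. Imputation and weighting were not simulated.

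The stated 80% power for Hypothesis 1a is not reached at 6 and 10 points on 6 df. It is about 60-68% (7% v 1%) and 64-66% (15% v 5%), of which about 15 points of loss is due to the degrees of freedom. It would go too far to attribute the whole gap at 7% v 1% to the reference distribution.

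**What to change.** Before analysis, prespecify one small-cluster method with its matching interval for Hypothesis 1a and the other binary outcomes. Either of these would serve:

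- GEE with a named bias-corrected sandwich variance and a t reference on 6 df. Kauermann-Carroll ran close to 5% here; Mancl-DeRouen is valid but conservative.
- A school-level t-test on 6 df applied to covariate-adjusted residuals.

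Check the chosen method by simulation with the final covariates, imputation and any weights.

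Restate the Hypothesis 1a power sentence on 6 df. For 80% power the detectable decrease is about 11.4-11.6 points from 15%. From 7% it is about 6.4 to 7 points, which means near-zero incidence in the intervention arm.

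The cost is SAP wording and a few lines of code, with no change in enrolment. Intervals are about 1.44 times as wide as uncorrected ones (about 1.66 times with Mancl-DeRouen), and the stated power is less favourable.
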